#### **5.8.2.6. Iron-Related Parameters**

Iron metabolism parameters including serum iron, total iron binding capacity (TIBC), transferrin, soluble transferrin receptor, ferritin, and hepcidin will be taken at Day 1 of Cycle 1 and every 4 subsequent cycles, EOT, PTFU and EOS visits. Descriptive statistics of observed values, absolute and percentage change from baseline values at each postbaseline visit will be presented.

Shift analyses will also be performed to summarize serum ferritin EOT change from baseline. Serum ferritin will be grouped into three categories:  $< 300$ ,  $\geq 300$  and  $< 1000$ ,  $\geq 1000$  ( $\mu\text{g/L}$ ).

Plots of iron parameters for both mean observed values and mean absolute change from baseline over time will be presented.

#### **5.8.2.7. Erythropoietin and Immature RBC Parameters**

Blood samples relating to erythropoietin parameters including serum erythropoietin levels, reticulocytes and nucleated RBCs will be taken at Day 1 of Cycle 1 and every 4 subsequent cycles, EOT, PTFU and EOS visits. Descriptive statistics of observed values, absolute and percentage change from baseline values at each postbaseline visit will be presented. Plots of erythropoietin parameters for mean observed values, mean change and mean percentage change from baseline over time will be presented.

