Anemia is the predominant cytopenia observed in MDS and is present in 85% of MDS patients at the time of diagnosis.¹⁴ Refractory anemia resulting from ineffective erythropoiesis is a major cause of morbidity and mortality in MDS patients.¹⁵ Supportive care with blood transfusions, erythropoiesis stimulating agents (ESAs), and other growth factors are used to treat anemia.

Clinical studies have demonstrated that ESAs can provide clinical benefit to MDS patients by reducing the need for RBC transfusions. Only one third of unselected patients treated with ESAs have an erythroid response.^{16,17} A significant number of MDS patients have serum EPO levels in excess of 500 U/L, indicating the anemia in MDS is not a consequence of endogenous EPO deficiency and unlikely to respond to exogenous EPO.¹⁸ This observation suggests that impaired erythropoiesis in MDS patients occurs downstream of the steps that are regulated by EPO. Ineffective erythropoiesis leading to anemia in MDS patients appears to be associated with intramedullary apoptosis of cells during the later stages of erythrocyte development beyond those regulated by EPO.^{19,20}

The azanucleosides, azacitidine (Vidaza[®]) and decitabine (Dacogen[®]), and lenalidomide (Revlimid[®]) have demonstrated activity in patients with MDS.^{21,22} A randomized phase 3 trial comparing azacitidine with best supportive care (BSC) demonstrated hematologic improvement, delayed progression to AML or death and improved quality of life.²³ A second phase 3 trial demonstrated improved 2-year overall survival.²⁴ A phase 3 study comparing decitabine with BSC showed improved overall response rate (ORR) and progression-free survival (PFS).²⁵

MDS represents a significant hematologic malignancy of the elderly population, contributing to serious comorbidities and increased health care use and cost. Given the high prevalence of cardiac and other comorbidities in this patient population, and the strong association between comorbidities, transfusional support, and iron overload, strategies to improve anemia and maintain adequate iron balance are critical in managing patients with MDS.⁴

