**Baseline EPO and Other Lab Parameters**

Baseline erythropoietin (EPO) is defined as the maximum test value within 28 days of Cycle 1 Day 1.

For all other lab parameters, baseline is defined as the last observation on or prior to Cycle 1 Day 1.

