## **5.2. General Considerations**

Unless otherwise noted, continuous data will be summarized with the following descriptive statistics: number of observations (n), mean, standard deviation (STD), median, minimum and maximum. Categorical data will be summarized with frequencies (n) and percentages (%). In cases where missing data cause percentages not to sum to 100, a missing data row will be provided. Percentages will use column totals as the denominator unless otherwise indicated. For time to event variables, the Kaplan-Meier curves will be presented if the number of patients is more than 5.

All study data will be included in study data listings. Missing data will generally not be imputed, unless otherwise stated.

Data summaries may also be presented for LTB and HTB patients separately as specified. All summaries will be descriptive. No formal hypothesis testing is planned.

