#### **5.8.2.9. Hemolysis-Related Parameters**

Hemolysis-related parameters include direct bilirubin, total bilirubin, and lactate dehydrogenase (LDH). Descriptive statistics of observed values, absolute and percentage change from baseline values at each postbaseline visit will be presented. Plots of hemolysis-related parameters for both mean observed values, mean change and mean percentage change from baseline over time will be presented.

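### Mean percentage change is biased upward with no drug effect for laboratory markers whose baseline is a single value; for EPO the maximum-value baseline pulls the other way

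*SAP*

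**What the plan says.** **Tables.** For the iron markers SAP 5.8.2.6 plans: "Descriptive statistics of observed values, absolute and percentage change from baseline values at each postbaseline visit will be presented". Sections 5.8.2.7 (EPO, reticulocytes, nRBC) and 5.8.2.9 (bilirubin, LDH) carry the same sentence. Under SAP 5.2 the default summary is "number of observations (n), mean, standard deviation (STD), median, minimum and maximum", so each table shows the median beside the mean.

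**Plots.** These differ by group.
- EPO, reticulocytes and nRBC: "Plots of erythropoietin parameters for mean observed values, mean change and mean percentage change from baseline over time will be presented".
- Hemolysis: "Plots of hemolysis-related parameters for both mean observed values, mean change and mean percentage change from baseline over time will be presented".
- Iron: "Plots of iron parameters for both mean observed values and mean absolute change from baseline over time will be presented". There is no percentage plot.

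**Baseline.** SAP 5.1 sets EPO apart: "Baseline erythropoietin (EPO) is defined as the maximum test value within 28 days of Cycle 1 Day 1". All other laboratory parameters use the last observation on or before Cycle 1 Day 1. Patients who roll over without interruption keep their Study A536-03 baseline (SAP 5.1). In that study EPO was scheduled at both Screening and Cycle 1 Day 1 (SAP Appendix 2). Study A536-05 schedules it before dosing only at Cycle 1 Day 1 (SAP Appendix 3).

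**Setting.** All summaries are descriptive with no hypothesis test (SAP 5.2), and no comparison with controls is planned (Protocol 15.2.3). Geometric means are specified for drug concentrations (SAP 5.9.3) but not for these markers.

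**The concern.** A percentage change divides by the patient's own baseline reading. A baseline that happens to be low inflates the ratio by more than an equally displaced high baseline deflates it. The arithmetic mean of such ratios is therefore above zero even when nothing has changed. A randomised trial would largely cancel this in the difference between arms. Here every summary is a within-patient change in one uncontrolled group, so the bias is read as change on treatment.

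Iron metabolism, EPO and reticulocytes belong to a stated secondary objective (SAP 2). For single-value-baseline markers an upward bias would exaggerate a rise or mask part of a fall. For EPO, taking the highest pre-dose value as reference creates a second artefact in the opposite direction. The plotted EPO percentage change would then mix the two, with a sign that cannot be known in advance.

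**Working it through.** The plan gives no SD, expected change or sample size calculation for these markers, so there is no figure to reproduce. The check asks what the planned statistic shows when the drug does nothing.

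**Inputs.** Baseline rules come from SAP 5.1 and the EPO sampling times from SAP Appendices 2 and 3. The within-patient log-scale SD, s, is in neither document. It is an assumption, shown over a range. The model is a log-normal marker with independent within-patient errors and no drug effect.

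**Single-value baseline.** The log ratio of visit to baseline is N(0, 2s²), so

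mean percentage change = exp(s²) − 1.

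For example, at s = 0.2, exp(0.04) − 1 = 4.1%; at s = 0.5, exp(0.25) − 1 = 28.4%. The median change is 0, the geometric mean ratio is 1.00 and the mean absolute change is 0 at every s.

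**EPO with the larger of two pre-dose values as baseline.** The mean of exp(−max) for two independent N(0, s²) values is 2·exp(s²/2)·Φ(−s/√2). Multiplying by exp(s²/2) for the visit value gives

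mean percentage change = 2·exp(s²)·Φ(−s/√2) − 1.

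At s = 0.5: 2 × 1.284 × 0.3618 − 1 = −7.1%. The expression crosses zero at s ≈ 0.68.

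| s (assumed) | Single value: mean | Single value: median | Max of two: mean | Max of two: median |
|---|---|---|---|---|
| 0.1 | +1.0% | 0 | −4.7% | −5.4% |
| 0.2 | +4.1% | 0 | −7.6% | −10.5% |
| 0.3 | +9.4% | 0 | −9.0% | −15.5% |
| 0.5 | +28.4% | 0 | −7.1% | −24.1% |
| 0.7 | +63.2% | 0 | +1.3% | −32.3% |

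Simulation of 1,000,000 patients per setting agreed with both formulas and supplied the max-of-two medians.

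**Mixed EPO baselines.** If half the patients have two pre-dose values and half have one, the null mean is −1.8% at s = 0.2, +0.2% at 0.3, +4.3% at 0.4 and +10.7% at 0.5. The actual share is not in the documents.

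**Does a log-scale summary repair EPO by itself?** No. The expected maximum of two N(0, s²) values is s/√π, so the null geometric mean ratio is exp(−s/√π). At s = 0.2 this is exp(−0.113) = 0.893, and at s = 0.5 it is exp(−0.282) = 0.754. A spurious fall remains.

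**Does between-patient spread matter?** With between-patient log-SD of 0.5, 1.0 or 1.5 and no within-patient variation, the mean percentage change is 0.0%. The cause is noise in the baseline denominator.

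**nRBC.** These counts can be zero. A zero baseline has no percentage change at all, so the log-normal figures do not size the effect for nRBC.

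**The case against.** The best defence is that this is presentation of untested, descriptive output. The tables give the median, which is unbiased for a single-value baseline. Every plot set that includes mean percentage change also shows observed means and mean change. Iron has no percentage plot, and ferritin also has a shift table and a maximum-decrease summary. If s is 0.1 to 0.2 the bias is only 1% to 4%. All of this stands and limits the weight of the point. It does not rescue the hemolysis and reticulocyte percentage plots, which show only means.

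A reader might go further and infer that skewed markers rise by chance in all three groups, EPO included, so that a drug effect appears where there is none. The documents do not support that, for three reasons.
- Skew between patients gives no bias. The evidence of wide spread, such as the Protocol 7.1 remark that "A significant number of MDS patients have serum EPO levels in excess of 500 U/L", the EPO cut-points and the ferritin classes, says nothing about s.
- For EPO the maximum-value baseline tends to produce a fall in patients with two pre-dose values.
- Nothing is tested, and the size rests on an s that the documents do not give.

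A reader might also infer that a true fall in ferritin or hepcidin would be hidden. The unbiased median and the absolute-change plots make that unlikely.

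**Conclusion.** The point holds in limited form. For iron, hemolysis markers and reticulocytes, the arithmetic mean percentage change is biased upward under no effect by exp(s²) − 1, roughly 1% to 28% for s from 0.1 to 0.5. This assumes log-normal values and independent within-patient errors. The bias reaches the tables for all three groups, but the plots only for the hemolysis and reticulocyte/nRBC sets. For nRBC the mechanism is the same where baseline is positive, but the size cannot be given from this model.

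For EPO no general upward bias can be claimed. In roll-over patients with two pre-dose values inside the window, the null mean is negative below s of about 0.68. The null median is −10.5% to −24.1% for s from 0.2 to 0.5. How far this shows in the pooled EPO summary depends on how many patients have two values.

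This is a worthwhile, inexpensive improvement to secondary descriptive output. It does not threaten the primary safety objective.

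**What to change.** 1. **Ferritin, hepcidin, soluble transferrin receptor, LDH, bilirubin and reticulocytes:** report the geometric mean ratio to baseline (the exponential of the mean log ratio) with a 95% CI at each visit. Plot it in place of mean percentage change where that is now plotted (hemolysis and reticulocytes). Keep the tabulated medians and ranges. The iron figures need no percentage-plot change.
2. **nRBC:** plot the median change, because zero values have no logarithm.
3. **EPO:** make the same change, but only together with a new reference for change from baseline: the last pre-dose value, or the average of the pre-dose values. Take any average on the log scale, so that the ratio stays at 1 under no effect. State that only pre-dose values count, since the 28-day window in SAP 5.1 does not say so.

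The cost is a small revision of table and figure shells and one changed EPO derivation, all on data already collected. The downside is that zero values cannot be log-transformed, so the SAP needs a stated rule for any that occur in the other markers.

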#### **5.8.2.8. Bone Metabolism Parameters**

Bone metabolism parameters including bone specific alkaline phosphatase (BSAP) and serum C-telopeptide of type I collagen (CTX) will be taken at Cycle 1 Day 1, Cycle 4 Day 1, and EOT visits. Descriptive statistics of observed values, absolute and percentage change from baseline values at each postbaseline visit will be presented.

#### **5.8.2.9. Hemolysis-Related Parameters**

Hemolysis-related parameters include direct bilirubin, total bilirubin, and lactate dehydrogenase (LDH). Descriptive statistics of observed values, absolute and percentage change from baseline values at each postbaseline visit will be presented. Plots of hemolysis-related parameters for both mean observed values, mean change and mean percentage change from baseline over time will be presented.

### 5.8.2.10. Other Analysis

For the following continuous variables, the descriptive statistics including mean, standard deviation, median and range will be presented:

- Maximum reduction over rolling 8-week intervals (absolute and percentage) in transfusion burden from baseline in HTB patients
- Maximum increase in hemoglobin level from baseline in LTB patients
- Maximum hemoglobin mean change from baseline during any rolling 8-week period in LTB patients
- Maximum decrease/percentage decrease in serum ferritin
- Change in absolute reticulocytes
- Change in pre-transfusion hemoglobin level in HTB patients
- Frequency of RBC transfusions in HTB patients

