15.2.3. Secondary Analysis

Efficacy/Pharmacodynamic Effects Analysis of Secondary Endpoints:

All efficacy analyses will be performed for the EE and mITT populations.

Efficacy will be evaluated by determining the proportion of patients who have a modified HI-E erythroid response rate based upon the IWG 2006 criteria ([Appendix 5](#)), defined as 1) A mean hemoglobin increase ≥ 1.5 g/dL over an 8-week period as compared to baseline, not influenced by RBC transfusion in NTD patients or 2) A decrease of ≥ 4 units or $\geq 50\%$ of units of RBCs transfused over a period of 8 weeks, relative to the number of units of RBCs transfused in the 8 weeks immediately prior to Cycle 1 Day 1 in TD patients.

Baseline hemoglobin will be the average of two or more measures (not influenced by RBC transfusion) performed during the screening period for study A536-03 (for patients without interruption) or study A536-05 (for patients with interruption).

Baseline units of RBCs transfused will be the 8-week period prior to study A536-03 (for patients without interruption) or study A536-05 (for patients with interruption).

The erythroid response will be summarized using both a point estimate and its exact 95% confidence interval based on binomial distribution.

No direct comparison testing with concurrent or historical controls will be performed.

Analysis of other secondary efficacy/pharmacodynamic endpoints will include:

- Time to HI-E response and duration of HI-E response as per the IWG 2006 criteria and modified IWG criteria.
- Mean RBC transfusion burden
- Rate of RBC transfusion-free period lasting \geq 8 weeks in TD patients.
- Mean hemoglobin level change in NTD patients
- Other PD endpoints including:
 - Biomarkers for iron overload/metabolism
 - Relationship of biomarkers to response
 - Rates of HI-E, HI-N and HI-P

Exploratory endpoints will include:

- Biomarkers related to the TGF β superfamily.
- Patient-reported quality of life using tools including but not limited to the FACT-An questionnaire.

All binary endpoints will be summarized using both a point estimate and its exact confidence interval based on the binomial distribution. The time-to-event type secondary endpoints will be analyzed using Kaplan-Meier method to estimate the survival curve and median time to event and 95% confidence interval.

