## 2. STUDY OBJECTIVES

Primary Objective:

- To evaluate the long-term safety and tolerability of ACE-536 in patients with low or intermediate-1 risk MDS who were previously enrolled in study A536-03.

Secondary Objectives:

- To evaluate erythroid response (modified HI-E from International Working Group [IWG] 2006 criteria), defined as proportion of patients with:
  - A mean hemoglobin (Hgb) increase  $\geq 1.5$  g/dL over an 8-week period as compared to baseline, not influenced by red blood cell (RBC) transfusion, in non-transfusion dependent (LTB) patients (refer to [Section 5.1](#) for definitions of LTB and HTB).
  - A decrease of  $\geq 4$  units or  $\geq 50\%$  of units of RBCs transfused over a period of 8 weeks, relative to the 8 weeks immediately prior to Day 1, in transfusion dependent (HTB) patients.
- To evaluate rates of erythroid, neutrophil and platelet (HI-E, HI-N and HI-P) responses (IWG 2006 criteria)
- To evaluate the rate of RBC transfusion independence lasting  $\geq 8$  weeks in HTB patients
- To evaluate time to HI-E response and duration of HI-E response (modified and non-modified IWG 2006 criteria)
- To evaluate the mean change in RBC transfusion burden in HTB patients and mean change in hemoglobin levels in LTB patients
- To evaluate the pharmacokinetic (PK) profile of ACE-536
- To evaluate other pharmacodynamic (PD) effects (e.g., iron overload/metabolism, erythropoietin [EPO], and reticulocytes)

Exploratory Objectives:

- To examine biomarkers related to the TGF- $\beta$  superfamily

- To examine self-reported quality of life using tools including but not limited to the FACT-An questionnaire

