#### 3.1. Study Design

Patients in all cohorts will receive ACE-536, administered subcutaneously (SC), every 3 weeks for up to 87 cycles or up to 1825 days, whichever occurs first. Dose titration(s), delay(s) and dose reduction(s) may be required for individual patients as outlined in the Individual Dose Modification Rules (protocol Section 10.8).

The base study A536-03 is a phase 2, open-label, ascending dose study to evaluate the effects of ACE-536 on anemia in patients with low or intermediate-1 risk MDS who are not currently receiving treatment with an erythropoiesis-stimulating agent (ESA). A total of up to 153 patients may be enrolled in the base study A536-03 and may be eligible for study A536-05.

Consenting patients that meet the A536-05 eligibility criteria may immediately roll over from A536-03 to study A536-05. These patients will forego the Post-Treatment Follow-up (PTFU) and End of Study (EOS) visits of A536-03 to begin study A536-05. For these patients, C1D1 of A536-05 may take place 28 ( $\pm$  7) days after the last dose administered in the base study A536-03, which may coincide with the patient's A536-03 End of Treatment (EOT) visit. These patients will be considered "patients without treatment interruption." Patients enrolled in expansion cohorts 2 and 3 in Study A536-03 must meet the "patients without treatment interruption" criteria to be considered for the A536-05 study, unless otherwise prospectively approved by the sponsor.

Patients who complete the EOS visit for the base study A536-03 prior to C1D1 of A536-05 are considered "patients with treatment interruption." These patients will have a 28-day screening period to allow them to be re-assessed for eligibility by meeting additional inclusion criteria, as defined in protocol Section 9.2.

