### **5.8.7. Laboratory Evaluations**

Results from the following laboratory parameters, recorded at their respective time points will be summarized by time point:

**Hematology** (Screening, Day 1 of each cycle, End of Treatment, Post Treatment Follow Up and End of Study): RBC, white blood cell (WBC) with differential, hemoglobin, hematocrit, reticulocyte count, platelet count, mean corpuscular volume (MCV), mean corpuscular hemoglobin (MCH), mean corpuscular hemoglobin concentration (MCHC), red blood cell distribution width (RDW), and nucleated RBCs (nRBCs)

**Chemistry** (Screening, Day 1 of Cycle 1 and Day 1 of every other subsequent cycles, End of Treatment and End of Study): Sodium, potassium, aspartate aminotransferase (AST), alanine aminotransferase (ALT), lactate dehydrogenase (LDH), total bilirubin, direct bilirubin, alkaline phosphatase, blood urea nitrogen (BUN)/urea, creatinine, gamma-glutamyl transpeptidase (GGT), calcium, phosphorus, glucose, amylase, lipase, total protein, albumin, and uric acid

**Urine Analysis** (Day 1 of Cycle 1 and every 4 subsequent cycles, End of Treatment and End of Study): pH, specific gravity, protein, glucose, ketones, blood, leukocyte esterase, nitrite, microscopic examination (if performed)

**Urine Chemistry** (Day 1 of Cycle 1 and every 4 subsequent cycles, End of Treatment and End of Study): Microalbumin and creatinine; albumin/creatinine ratio

Categorical and numeric variables will be presented separately. Actual values and changes in hematology and biochemistry laboratory values from baseline will be summarized by time point. Shift tables for the hematology and biochemistry laboratory parameters comparing values above, within and below the normal reference range at baseline to the end of treatment visit will be presented using standard reference ranges.

Peripheral blood smears are taken at Screening, Day 1 of Cycle 1 and every 4 subsequent cycles, and at the end of treatment visit. These data will be listed only.

All laboratory values will be listed for all patients.

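### Mean hemoglobin change in LTB patients is a secondary objective, but the SAP's only continuous LTB-specific hemoglobin-change variables are per-patient maxima, and SAP 5.13 does not declare the omission

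*SAP*

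**What the plan says.** SAP Section 2 sets as a secondary objective "To evaluate the mean change in RBC transfusion burden in HTB patients and mean change in hemoglobin levels in LTB patients". Protocol 8.2 has the same objective in NTD/TD terms, and Protocol 15.2.3 lists "Mean hemoglobin level change in NTD patients" among the secondary analyses. SAP 5.13 states that LTB/HTB replaces NTD/TD, so the group is the same.

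The SAP treats hemoglobin in LTB patients in three places:

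- **5.8.2.1 and 5.8.2.3** (modified HI-E and HI-E) report proportions of responders against a 1.5 g/dL threshold.
- **5.8.2.10** gives descriptive statistics for "Maximum increase in hemoglobin level from baseline in LTB patients" and for "Maximum hemoglobin mean change from baseline during any rolling 8-week period in LTB patients".
- **5.8.7**, the safety laboratory section, lists hemoglobin under hematology and says: "Actual values and changes in hematology and biochemistry laboratory values from baseline will be summarized by time point". It mentions no transfusion-burden split. Under 5.2, "Data summaries may also be presented for LTB and HTB patients separately as specified", and 5.8.7 specifies none.

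The rule dropping hemoglobin values within 7 days after an RBC transfusion is in SAP 5.8 and is worded for the efficacy analysis. Protocol 15.5 requires departures from the protocol's analyses to be indicated in the SAP. SAP 5.13 does this for the dropped time to and duration of modified HI-E, the dropped EE population and the revised hemoglobin baseline. It does not mention mean hemoglobin change.

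**The concern.** A mean change and a maximum change answer different questions. The mean change describes the typical shift from baseline. The maximum is the best value a patient ever reached: it picks up favourable random variation and has more chances to do so the longer the patient is observed. Observation time varies widely here, because dosing is "every 3 weeks for up to 87 cycles or up to 1825 days, whichever occurs first" and patients can stop early.

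Entry route matters too. Under SAP 4.1, direct rollovers contribute A536-03 data and interrupted patients do not. The A536-03 schedule (SAP Appendix 2) has hematology about weekly, against Day 1 of each cycle in A536-05. Two LTB patients with the same underlying hemoglobin course could therefore have different expected maxima because of follow-up length and entry route.

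At stake is how this secondary objective is reported. If the maxima are the only continuous LTB figures available, they may be read as the size of the effect.

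**Working it through.** The plan states no figure to reproduce: there is no sample-size calculation and no hypothesis test. The check asks what each variable would average if the drug did nothing.

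**Inputs from the documents**
- Visits: one every 21 days, at most 87 (1825/21 = 86.9). I used 5, 30 and 87 to represent short, medium and full follow-up.
- Baseline: the average of values within 28 days of C1D1 (SAP 5.1), taken as the mean of two.
- Rolling 8-week period: SAP 5.8.2.3 runs it between measurement dates at least 8 weeks apart. With 3-weekly visits that needs 4 visits (3 × 3 = 9 weeks).

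**Assumptions, not in the documents**
- Within-patient SD 0.5 to 1.0 g/dL.
- Correlation between successive visits 0 to 0.7.
- Stable, normally distributed hemoglobin with no trend (AR(1)).

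**Maximum single increase, independent visits.** The baseline error averages to zero, so the expected maximum change is SD × e(k), where e(k) is the expected largest of k standard normal values: e(5) = 1.163, e(30) = 2.043, e(87) = 2.457.
- SD 0.5: 0.58, 1.02 and 1.23 g/dL.
- SD 1.0: 1.16, 2.04 and 2.46 g/dL.

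**Maximum rolling mean, 5 independent visits.** There are two overlapping windows, whose means differ by (y5 − y1)/4. The expected larger one is ½ × √(2/π) × √2 × SD/4 = 0.141 × SD, which is 0.07 at SD 0.5 and 0.14 at SD 1.0.

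**With correlation.** Simulation under no effect gives these averages in g/dL. Each cell runs from correlation 0 to correlation 0.7.

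| Variable | SD | 5 visits | 30 visits | 87 visits |
|---|---|---|---|---|
| Maximum single increase | 0.5 | 0.58 to 0.39 | 1.02 to 0.89 | 1.23 to 1.15 |
| Maximum single increase | 1.0 | 1.16 to 0.79 | 2.05 to 1.80 | 2.45 to 2.29 |
| Maximum rolling mean | 0.5 | 0.07 to 0.06 | 0.44 to 0.59 | 0.57 to 0.83 |
| Maximum rolling mean | 1.0 | 0.14 to 0.13 | 0.88 to 1.19 | 1.13 to 1.67 |
| Ordinary mean change | any | 0 | 0 | 0 |

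The simulated ordinary mean change was within 0.01 g/dL of 0 throughout. Correlation lowers the single-value maximum. From 30 visits on it raises the rolling-mean maximum, because averaging neighbouring visits then removes less noise.

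**What the model leaves out.** Weekly A536-03 values would raise the maxima for rollovers. Dose holding at high hemoglobin and stopping after sustained decline are not modelled. Nor is regression to the mean from the entry hemoglobin limit, which would also move an ordinary mean change above zero.

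**The case against.** The strongest reply is that the objective is already served. SAP 5.8.7 tabulates hemoglobin change from baseline by time point in a safety population identical to the ITT population. SAP 5.2 permits LTB and HTB summaries separately, and complete hemoglobin records are listed for each patient. This stands in part. It would be too strong to infer that the objective goes wholly unanswered, or that the SAP commits to pooling the groups. What 5.8.7 lacks is an LTB split and the 7-day post-transfusion exclusion. Both matter: HTB patients receive at least 4 units per 8 weeks, and LTB patients may receive up to 3.

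A second reply is that the SAP never says the maxima replace the mean change. They sit under other analyses, are named as maxima and are purely descriptive. That is correct. Substitution is a reader's inference, and the documents show only that one analysis is absent and the others are present.

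A third reply is that 5.13 claims to list only major changes. But it does list dropping time to and duration of modified HI-E, which is a comparable secondary item.

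Finally, a table by visit does not remove dependence on follow-up, because later visits describe only those still on treatment. This stands, and it is why n must be shown.

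**Conclusion.** The point holds. A secondary objective that the protocol lists as an analysis has no LTB-specific mean-change analysis in the SAP. The only continuous LTB-specific hemoglobin-change variables are maxima, and 5.13 does not record the omission. The qualifiers matter, because the HI-E endpoints are also LTB-specific but are responder proportions.

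The direction of the bias is certain for a stable process: both maxima have no-effect expectations above zero that rise with visit count. Its size rests on the assumed SD and correlation. Over the stated ranges it is about 0.4 to 1.2, 0.9 to 2.0 and 1.2 to 2.5 g/dL for the single-value maximum at 5, 30 and 87 visits. For the rolling-mean maximum it is about 0.1, 0.4 to 1.2 and 0.6 to 1.7.

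A reader might infer that no-effect data would show a gain of about 1.5 g/dL, the plan's own response threshold. The documents do not support a single figure. The single-value maximum reaches 1.5 only for some SDs and longer follow-up. The rolling-mean maximum does so only at 87 visits with SD of about 0.9 to 1.3.

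The primary objective is safety and no test depends on these variables, so the consequence is confined to the reporting of this secondary objective.

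**What to change.** In SAP 5.8.2.10, add for LTB patients the mean change in hemoglobin from baseline by visit, with n and 95% CI, excluding values within 7 days after RBC transfusion. State how A536-03 visits are numbered for direct rollovers, since SAP 4.1 includes their data. Label the two maxima as supportive. Record in 5.13 any departure from the protocol that remains. Averages over fixed early periods would be a reasonable addition but are optional.

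The cost is one extra table from data already collected. The reported gain will be smaller than the maxima suggest. Means at later cycles will describe only patients still on treatment, so n must appear at every visit.
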